1.0 Objectives

Primary Aim: To determine whether synthetic retropubic midurethral sling (MUS) combined with concomitant detrusor injections of onabotulinumtoxinA is more effective than midurethral sling alone in improving mixed urinary incontinence (MUI) symptoms.

Secondary Aims:

a. To compare incontinence episode frequency on a 3-day diary in women who undergo midurethral sling plus onabotulinumtoxinA to those who undergo midurethral sling alone.

b. To compare urinary incontinence symptoms and quality of life in women who undergo midurethral sling plus onabotulinumtoxinA to those who undergo midurethral sling alone.

c. To identify baseline factors associated with persistent urgency incontinence in women after midurethral sling alone and midurethral sling plus onabotulinumtoxinA.

Hypotheses:

1. By using a double-blind randomized controlled trial, we will be able to show that retropubic midurethral sling surgery with detrusor muscle onabotulinumtoxinA injection will be more effective at controlling mixed urinary incontinence symptoms than sling surgery alone.

2. Patients who receive both midurethral sling and onabotulinumtoxinA injection will have objectively have fewer incontinence episodes than those who receive midurethral sling alone

3. Patients who receive both treatments will have better quality of life as it relates to urinary symptoms than those who receive midurethral sling alone

4. Patients who have persistent urgency urinary incontinence after either midurethral sling alone or both midurethral sling and onabotulinumtoxinA injection alone will have significantly different baseline urine microbial content than those who do not have persistent urgency symptoms after treatment

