3.0 Inclusion and Exclusion Criteria

All women with MUI planning surgical intervention with midurethral sling will be approached for study participation. MUI will be defined as an answer of "moderately' or "quite a bit" bothered to Urinary Distress Inventory (UDI) items (2) "urine leakage with a feeling of urgency" AND (3) "urine leakage related to coughing, sneezing, or laughing". $PROTOCOL \ TITLE: \ \text{The SLIM Study: } \underline{Sl} \text{ing and Botox} \\ \textcircled{B} \ \underline{Injection for } \underline{M} \text{ixed Urinary Incontinence}$

Enrolled participants must meet all the following criteria:

- Undergoing mid-urethral sling surgery
- Have symptoms of both stress and urgency urinary incontinence
- Able to consent, fill out study documents, and complete all study procedures and follow-up visits
- At least 18 years of age
- English speaking
- Be able and willing to learn clean intermittent self catheterization technique

Women will be excluded for any of the following reasons:

- History of recurrent UTI (defined as three culture proven UTIs within last 12 months)
- Systemic neuromuscular disease known to affect the lower urinary tract
- Undergoing concomitant prolapse surgery
- Previous incontinence surgery
- Treatment with anticholinergic medication in the last 2 months
 - Darifenacin/Enablex
 - Oxybutynin IR/Ditropan
 - Oxybutynin ER/Ditropan XL
 - Oxybutynin Patch/Oxytrol
 - Oxybutynin Gel/Gelnique
 - Solifenacin/Vesicare
 - Tolterodine IR/Detrol
 - Tolterodine ER/Detrol LA
 - Trospium IR/Sanctura
 - Trospium ER/Sanctura XR
 - Fesoterodine/Toviaz
 - Mirabegron/Myrbetriq
- Previous bladder injection with onabotulinumtoxinA
- Prisoner status
- Pregnancy
- Patients on SGLT2 Inhibitors
 - (canagliflozin, dapagliflozin, and empagliflozin)

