5.0 Study Endpoints

Primary endpoint will occur at 3 months. Secondary endpoint is at 1 year, or when the subject completes her 1 year post-operative visit.

6.0 **Procedures Involved**

Women with MUI undergoing midurethral sling for bothersome SUI will be randomized to 100 units onabotulinumtoxinA or placebo (saline) injections in the detrusor at the time of sling surgery. Specifically, the retropubic midurethral slings used will be either the Gynecare TVT Exact Continence System by Ethicon or the Boston Scientific Advantage Fit Transvaginal Mid-Urethral Sling System based on surgeon preference. Surgeons and participants will be masked to study assignment. Primary outcome will be the Patient Global Assessment of Improvement (PGI-I), a global, patient oriented measure that assesses symptoms of SUI and UUI at 3-months. The primary outcome, PGI-I asks subjects to best describe how their urinary tract condition is now, compared to how it was before treatment for urinary leakage. Response choices are: (1) 'very much better', (2) 'much better', (3) 'a little better', (4) 'no change', (5) 'a little worse', (6) 'much worse', and (7) 'very much worse'. Construct validity of the PGI-I was demonstrated in incontinence trials.32

We selected a subjective, patient oriented outcome as our primary outcome measure secondary to the complex nature of MUI, and the association between dissatisfaction after incontinence surgery and persistent or new onset urgency. We felt the patient's overall impression of their continence status represented a more clinically meaningful outcome than traditional objective measures. In addition, we will compare subjective and objective urinary symptoms and quality of life amongst treatment groups 3-months and 1-year after surgery.

All women with MUI planning surgical intervention with midurethral sling will be approached for study participation. MUI will be defined as an answer of "moderately' or "quite a bit" bothered to Urinary Distress Inventory (UDI) items (2) "urine leakage with a feeling of urgency" AND (3) "urine leakage related to coughing, sneezing, or laughing".

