Women will undergo standardized urologic evaluation at baseline including assessment of urinary symptoms and quality of life using short forms of the Urinary Distress Inventory (UDI-6) and Incontinence Impact Questionnaire (IIQ-7); assessment of overall severity of their incontinence symptoms with the Patient Global Impression of Severity (PGI-S);32 post void residual urine volume; urine analysis and culture; multichannel urodynamic testing; and pelvic exam with prolapse quantification using pelvic organ prolapse quantification system (POP-Q)33. All patients will also complete a 3-day urinary diary at baseline quantifying the number of incontinence episodes (stress and urge). Three months and 1-year after surgery, patients will again complete all baseline measures, including UDI, IIQ, PGI-I, PGI-S, and 3-day diary to report symptom and objective urinary symptoms after treatment. A sample of urine will be obtained for microbiome analysis at each visit.

Scheduled in-person follow-up visits will occur at baseline, 2 and 6-weeks, 3-months, and 1-year after surgery. At the baseline, 3-month, and 1-year visits,

 $PROTOCOL \ TITLE: \ \text{The SLIM Study: } \underline{Sl} \text{ing and Botox} \\ \textcircled{B} \ \underline{Injection for \ \underline{M} ixed \ Urinary \ Incontinence}$

research staff will collect the 3-day diary information and record any adverse events that have occurred during the post-operative period. Subjects will also complete the general and condition specific symptom and QOL questionnaires. In addition, an update of current medication and assessment as to whether any evaluation or treatment for pelvic floor disorders or adverse outcomes from surgery have occurred since the previous evaluation will be assessed by clinical staff at the in-person visits. All patient and survey data will be recorded in RedCAP.

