8.0 Data and Specimen Management

All analyses will be conducted using SPSS version 20 (Chicago, IL). Histograms will be used to determine distribution of data and appropriate non-parametric or parametric tests will be selected. Primary outcome will be analyzed dichotomously with responses of "very much better" and "much better" considered an optimal outcome. A chi-square test of association will be used to compare primary outcome (PGI-I) between treatment groups. Questionnaire data will be compared between sling alone and sling plus onabotulinumtoxinA groups using Mann Whitney test. All test results will be considered significant with a p-value of less than or equal to 0.05.

In a study of women with MUI undergoing retropubic midurethral sling, 66% of patients reported a PGI-I of "very much better' or 'much better' at 3-months.23 Similarly, in a randomized trial of intravesical onabotulinumtoxinA 55% of participants had PGI-I scores of "very much better' or 'much better'. Therefore, assuming "optimal outcomes' (PGI-I scores of "very much better' or 'much better' or 'much better) in 66% of women undergoing sling alone and 93% in those undergoing sling plus onabotulinumtoxinA, we will need to recruit 34 patients in each group

to show a significant difference with 80% power at a 0.5 significance level. Assuming a significant attrition rate, we will recruit approximately 100 women (50 in each arm).

Data will be collected at Northwestern Medicine. All study data will be recorded on Case Report Forms by research coordinator and securely maintained in a locked cabinet that only the study coordinator has access to. CRFs will be derived from source documentation and/or participant self-report. Data will be entered by the research coordinator at Northwestern into a REDCap database that will be stored on a secure sever. Only study staff will have passwords to access the project data on REDCap.

The data that is banked locally will be entered into an electronic data capture website. All users of REDCap need an institutional username and password to log in and to enter data. Research personnel, including study staff as well as study doctors will be able to collect and have access to subject data.

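### The between-arm tests for the secondary outcomes ignore baseline values the trial collects; a rank-ANCOVA with a rule for missing baselines would gain some power at little cost

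*Protocol*

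**What the plan says.** Secondary aim (a) in Protocol section 1.0 is "To compare incontinence episode frequency on a 3-day diary in women who undergo midurethral sling plus onabotulinumtoxinA" with women who have the sling alone. Hypothesis 2 is that the combined group will "objectively have fewer incontinence episodes than those who receive midurethral sling alone". Aim (b) covers urinary symptoms and quality of life. Section 6.0 gives the times: "In addition, we will compare subjective and objective urinary symptoms and quality of life amongst treatment groups 3-months and 1-year after surgery". It also sets out the data collection. UDI-6, IIQ-7, PGI-S and the diary are recorded at baseline, and then "Three months and 1-year after surgery, patients will again complete all baseline measures, including UDI, IIQ, PGI-I, PGI-S, and 3-day diary".

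The analysis text is in Protocol section 8.0. For questionnaires: "Questionnaire data will be compared between sling alone and sling plus onabotulinumtoxinA groups using Mann Whitney test". For everything else, including the diary: "Histograms will be used to determine distribution of data and appropriate non-parametric or parametric tests will be selected". The SAP lists the independent-samples t test, Mann-Whitney, chi-square and Wilcoxon signed rank, to be used as appropriate.

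Neither document names a baseline covariate, a regression or any adjusted model for a between-arm comparison. Neither says whether the analysed variable is the follow-up value or the change from baseline. Section 18.0 allows women to skip questionnaire items, and there is no rule for a missing baseline score.

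**The concern.** The trial collects the baseline value of each of these four outcomes and then leaves it out of the named between-arm tests. The Wilcoxon signed rank test does use baseline, but it is a within-woman test and does not adjust a comparison of arms. Where baseline predicts follow-up, conditioning on it removes variation unrelated to treatment, so a real difference is easier to detect with the same women. This matters more in a small trial, and this one was sized only for the PGI-I.

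The concern is about efficiency. The unadjusted tests carry no bias and no type I error problem. The primary outcome has no baseline value and is not involved.

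**Working it through.** **The plan's own figure.** The only sample size stated is for the primary outcome: 66% v 93%, 80% power, alpha 0.05, 34 per arm. The two-sided pooled formula without continuity correction gives

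n = [1.96·√(2 × 0.795 × 0.205) + 0.842·√(0.66 × 0.34 + 0.93 × 0.07)]² / 0.27² = 33.9, that is 34 per arm.

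The figure reproduces. No power, SD, correlation or effect size is given for any secondary outcome.

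**Inputs for the secondary outcomes**
- From the documents: 34 per arm evaluable (both documents); 39 per arm recruited (SAP); 50 per arm recruited (Protocol 8.0); alpha 0.05.
- Assumed: a difference of 0.5 SD; r from 0 to 0.7; for the protocol's 50 per arm, also a 15% loss (50 × 0.85 = 42.5, taken as 42).

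**Formula.** Adjusting for baseline multiplies the error variance by (1 − r²). Using the same rank efficiency, 3/π, for both tests:

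power = P(Z > 1.96 − 0.5/√[(2/n)(1 − r²)/(3/π)]), with r = 0 for Mann-Whitney on follow-up values.

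At n = 34 the Mann-Whitney standard error is √[(2/34)/(3/π)] = 0.248. Then 0.5/0.248 = 2.01 and power is 52.2%. At r = 0.5 the standard error is 0.248 × √0.75 = 0.215. Then 0.5/0.215 = 2.33 and power is 64.3%.

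| n per arm | Mann-Whitney | Adjusted, r = 0.1 | r = 0.3 | r = 0.5 | r = 0.7 |
|---|---|---|---|---|---|
| 34 | 52.2% | 52.6% | 56.0% | 64.3% | 80.5% |
| 39 | 57.8% | 58.3% | 61.9% | 70.2% | 85.6% |
| 42 | 61.0% | 61.4% | 65.1% | 73.4% | 88.0% |
| 50 | 68.5% | 69.0% | 72.6% | 80.5% | 92.8% |

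In sample-size terms, 1/(1 − r²) − 1 is a gain of 10% at r = 0.3 and 33% at r = 0.5.

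**Simulation.** The formula ignores ties, floors and counts, so the two tests were also simulated at 34 per arm. Six outcome shapes were used: normal, bounded, floored at zero, two counts and a 4-category ordinal score. There were 8,000 to 10,000 runs per cell, and r is the latent correlation. Change in power, in percentage points, relative to Mann-Whitney on follow-up values:

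| r | Rank-ANCOVA, complete baselines |
|---|---|
| 0 | −0.5 to 0.0 |
| 0.1 | −0.2 to +0.3 |
| 0.3 | +1.5 to +2.8 |
| 0.5 | +6.3 to +10.5 |
| 0.7 | +15.7 to +24.7 |

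A second set of assumed shapes gave 1–3, 3–9 and 9–28 points at r = 0.3, 0.5 and 0.7, so the gain also depends on the outcome's distribution. Type I error of rank-ANCOVA was 4.7–5.8%.

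**Missing baselines (10% assumed).** Dropping women without a baseline puts rank-ANCOVA 1.2–2.4 points below Mann-Whitney at r = 0.3. Filling with the median pooled over both arms restores gains of 1.3–2.5, 5.2–9.0 and 12.9–20.8 points at r = 0.3, 0.5 and 0.7, with type I error 4.7–5.6%. With 12% missing, more often at high baseline, type I error was 4.2–5.4%.

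**UDI-6.** Entry (Protocol 3.0) requires set levels of bother on two UDI items, which narrows the baseline spread. In an assumed one-factor six-item score this cuts r by 19–29%, for example from 0.48 to 0.39. UDI-6 probably gains least.

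**The case against.** The strongest reply is that nothing here is wrong. Mann-Whitney is a legitimate, pre-named test, and the alternative only improves secondary outcomes for which the trial was not sized. The gain rests on an assumed r, and the documents give some reason to expect a low one: entry restricts two UDI items, and an effective sling in both arms could floor the follow-up scores. At r of 0.3 or below the simulated gain is under 3 points. This stands, and it is why the size is given as a range.

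A second point is that the comparator is uncertain. Protocol section 2.0 speaks of greater improvement, which could mean change scores. Mann-Whitney on change has variance factor 2(1 − r) in place of 1. At 34 per arm its power is 39.8%, 52.2% and 73.9% at r = 0.3, 0.5 and 0.7, against 56.0%, 64.3% and 80.5% adjusted. The gain is then about 16, 12 and 7 points. The adjusted test is ahead under either reading, but the pattern across r differs, so the plan must say which variable is analysed.

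Third, the need for a missing-baseline rule arises from the fix, since a test on follow-up values needs no baseline, and the documents give no missing rate. That is true, and so the rule must accompany the fix.

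Fourth, a rank test reported beside a mean difference can disagree with it on significance. In simulation this happened in 6–9% of trials for normal, bounded and ordinal scores, 13–17% for a floored score and 17–27% for counts. This is a real cost, and the plan should say in advance which result decides.

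**Conclusion.** The concern holds. No between-arm test named in either document uses a baseline covariate, although the baseline of each of the four outcomes is collected. This is a recommended improvement to the secondary analyses; it does not correct an invalid test, and it leaves the primary analysis and the sample size untouched.

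Under the assumed 0.5 SD difference, 34 per arm and comparison of follow-up values, the benefit is small at r = 0.3, worthwhile at r = 0.5, large at r = 0.7, and nil or trivially negative at r near zero. The true r cannot be taken from the documents, so confidence in the size is moderate. Confidence in the direction is higher: with complete or median-filled baselines, the simulated downside at r = 0 is at most about half a point for complete data, and the adjusted test gains wherever r is 0.3 or more.

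**What to change.** In Protocol section 8.0 and the SAP:

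1. State that the follow-up value is the variable compared, as sections 1.0 and 6.0 suggest.
2. For UDI-6, IIQ-7, PGI-S and diary episodes, at 3 months and at 1 year, make the between-arm test a rank-ANCOVA: rank follow-up and baseline values over both arms together, regress ranked follow-up on arm and ranked baseline, and test arm.
3. Before ranking, fill a missing baseline with the median pooled over both arms, so that no woman with a follow-up value is dropped.
4. Keep Mann-Whitney on follow-up values as a sensitivity analysis, and signed-rank tests as within-arm description.
5. Report a baseline-adjusted mean difference with a 95% CI (HC3 standard error, t critical value). For the diary, report it in episodes with log(baseline + 1) as covariate. In simulation these intervals missed the true value in 4.1–5.0% of trials for scores and 3.5–5.7% for counts, against a nominal 5%. Log-link rate ratios for counts missed more often (5.0–11.0% depending on the interval), so label any rate ratio approximate and give it a bootstrap CI.
6. State in advance that the rank test decides and the CI is descriptive.
7. The SAP is written in the past tense. If the adjusted analysis is adopted after unblinding, label it post hoc.

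The cost is a short addition to each document, a few lines of code and some extra reporting. No new data are needed. The drawbacks are possible disagreement between test and interval, and little return if r proves low.

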## Statistical Analysis Plan

We based the sample size estimation off of previous studies assessing treatment of slings for mixed urinary incontinence and onabotulinumtoxinA injections for overactive bladder. A PGI-I response at 3 months postoperatively of "very much better" or "much better" was designated "improved." Assuming 66% of women in the placebo group and 93% in the onabotulinumtoxinA group were "improved" based on overall PGI-I scores, 68 women (34 in each arm) were needed to show a significant difference with 80% power at 0.05 significance level. If we assumed a 15% dropout rate, we aimed to recruit 78 participants (39 in each arm). R 3.6.3 was used for statistical analysis of the deidentified data. Independent samples t test, Mann-Whitney, x2, Wilcoxon signed rank sum statistical tests were used as appropriate.

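### Every test is judged at 0.05 with no multiplicity control or exploratory label, leaving a chance of roughly 16% to 49% of at least one false-positive secondary comparison if onabotulinumtoxinA adds nothing

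*Protocol*

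**What the plan says.** Protocol section 8.0 defines the primary analysis as one chi-square test of dichotomised PGI-I. It assigns the Mann-Whitney test to questionnaire data and then closes with a rule for everything: "All test results will be considered significant with a p-value of less than or equal to 0.05".

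Section 1.0 lists four numbered hypotheses. Hypothesis 1 concerns the primary aim. Hypotheses 2 and 3 claim fewer incontinence episodes and better urinary quality of life with the injection. Hypothesis 4 claims that women with persistent urgency incontinence after treatment "will have significantly different baseline urine microbial content" compared with women without it.

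Section 5.0 puts the primary endpoint at 3 months and adds: "Secondary endpoint is at 1 year". Section 6.0 is wider: "we will compare subjective and objective urinary symptoms and quality of life amongst treatment groups 3-months and 1-year after surgery". It lists UDI, IIQ, PGI-I, PGI-S and the 3-day diary as repeated at both times, and says the diary records stress and urge episodes.

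The SAP is one paragraph in the past tense. It gives the sample size, the software and a list of test types. It says nothing on multiplicity, testing order or the status of secondary results.

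**The concern.** The plan does not merely leave multiplicity open. It states a decision rule that gives every secondary test the same standing as the primary.

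Hypothesis 2 names its measure (diary episodes) but not the time point. Hypothesis 3 fixes neither the instrument nor the time point. Sections 5.0 and 6.0 do not settle the timing, since one places the secondary endpoint at 1 year and the other compares arms at both visits. Each hypothesis therefore has more than one chance to succeed. Under the rule as written, one p-value at or below 0.05 on any measure at either visit could be reported as support, even if PGI-I at 3 months shows no difference.

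At stake is how far the secondary conclusions on diary episodes, symptoms and quality of life can be trusted.

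**Working it through.** **1. The plan's own figure.** The SAP gives 66% against 93%, 80% power and a 0.05 level, and concludes that "68 women (34 in each arm) were needed". With the two-sided pooled-variance formula and no continuity correction:

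- mean proportion = (0.66 + 0.93)/2 = 0.795
- n per arm = [1.960 × √(2 × 0.795 × 0.205) + 0.842 × √(0.66 × 0.34 + 0.93 × 0.07)]² / 0.27²
- = [1.960 × 0.5709 + 0.842 × 0.5381]² / 0.0729 = 2.471 / 0.0729 = 33.9, so 34 per arm.

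The figure reproduces, with power of 80.1% at 34 per arm. Protocol section 8.0 prints the level as 0.5 for the same calculation. That level would need only 10 per arm, so 0.05 is the level behind the 34. The sample size rests on one test, and nothing below changes it.

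**2. How many secondary between-arm tests?** The documents give no count. From the measures in section 6.0:

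- UDI, IIQ, PGI-S and one diary count, at two times: 4 × 2 = 8
- adding PGI-I at 1 year: 9
- with the diary split into stress and urge: 5 × 2 + 1 = 11
- with total, stress and urge all tested: 6 × 2 + 1 = 13

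The range of 8 to 13 is therefore a reading of section 6.0, not a stated number. Section 2.0 also mentions surveys on pelvic floor function and sexual health. They are left out here and would raise the count.

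**3. Chance of at least one false positive if the drug adds nothing.** For k independent tests this is 1 − 0.95^k:

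- k = 8: 1 − 0.95^8 = 33.7%
- k = 9: 37.0%
- k = 11: 43.1%
- k = 13: 1 − 0.95^13 = 48.7%

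These scores come from the same women at two visits and overlap in content, so correlation is expected. The documents give no correlations. The table assumes equally correlated normal test statistics, each tested two-sided at 0.05.

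| Assumed correlation | 8 tests | 9 tests | 13 tests |
|---|---|---|---|
| 0 | 34% | 37% | 49% |
| 0.3 | 30% | 33% | 42% |
| 0.5 | 25% | 27% | 33% |
| 0.7 | 19% | 20% | 24% |
| 0.8 | 16% | 17% | 19% |

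**4. False positives favouring the drug only.** Hypotheses 2 and 3 are directional, so only a chance result in the drug's favour would be read as support. Each two-sided test at 0.05 puts 2.5% in that direction. For independent tests the chance is 1 − 0.975^k:

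- k = 8: 18.3%
- k = 13: 28.0%

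At correlation 0.8 the figures are about 8% (k = 8) and 10% (k = 13). The range is about 8% to 28%, against 2.5% for a single test.

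**5. Baseline factors and microbial content.** Aim c and hypothesis 4 fall under the same rule. The number of tests is not stated, so no error rate can be computed from the documents.

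**The case against.** The strongest reply is that the trial has one primary outcome, tested once, so its 5% error is intact. Secondary results are commonly read as supportive. The measures are correlated, and only results favouring the drug would be claimed. If the secondary endpoint is taken at 1 year only, as section 5.0 allows, four measures give at most 1 − 0.95^4 = 18.5% for any false positive and 1 − 0.975^4 = 9.6% for one favouring the drug.

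Much of this stands. The primary is unaffected, and the size depends on a count and correlations that the documents do not supply. But no text labels the secondary results as supportive, section 6.0 explicitly compares arms at both times, and even the 1-year-only reading at independence is well above the single-test level.

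Two stronger readings are tempting. A reader might infer that a false-positive secondary claim is likely, meaning more probable than not. Within 8 to 13 tests the chance stays below one half even at independence; it passes one half only at 14 or more nearly independent tests (1 − 0.95^14 = 51.2%). A reader might also infer that the microbial analysis is almost certain to give a spurious finding. The documents do not say that taxa will be tested one by one, and a single global comparison would fit hypothesis 4. That hypothesis also compares women with and without persistent urgency, not drug with placebo, so an error there would not be a false claim that the drug works.

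**Conclusion.** The point holds for the secondary analyses. The plan declares significance at 0.05 for every test, sets out formal secondary hypotheses, repeats several measures at two visits, and gives no hierarchy, adjustment or exploratory label.

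If onabotulinumtoxinA adds nothing, the chance of at least one false-positive secondary comparison is roughly 16% to 49%, and roughly 8% to 28% for one favouring the drug. This rests on 8 to 13 tests, counted from section 6.0, and on an assumed common correlation between 0.8 and 0. For the baseline-factor and microbial analyses, the plan leaves both the number of tests and the control of error unstated; no size can be given.

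The finding does not weaken the primary test or the 34 per arm.

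**What to change.** Replace the all-tests sentence in protocol section 8.0, and put the same text in the SAP, with:

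> The only confirmatory test is PGI-I at 3 months at two-sided 0.05. All secondary between-arm comparisons at 3 months and 1 year are exploratory and are reported as estimates with 95% CIs, without a claim of significance. If baseline microbial content is tested on more than one feature, one global test is done first and individual features are controlled at a 5% false discovery rate.

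The first sentence also makes the other baseline-factor analyses under aim c non-confirmatory.

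If results are not yet known and the sponsor wants confirmatory secondary claims, it should name one endpoint and one time point each for aims a and b, and test the two with Holm only after the primary succeeds. The choice should agree with section 5.0, which places the secondary endpoint at 1 year, and with the quality-of-life wording of aim b. The SAP is in the past tense. If results are already known, a hierarchy chosen now would not be prespecified, and the exploratory label is the credible option.

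The cost is wording in two documents, with no new data and no change in sample size. The downside is that fewer secondary results can be called significant.

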There is no high-quality evidence or consensus amongst specialists on how to approach treatment for women with MUI. The optimal treatment strategy for women with MUI is unclear. Historically, health care providers tried to identify which type of incontinence, stress or urgency, was most bothersome to the patient and treated the bothersome subtype first. Those with stress predominant incontinence underwent surgery, while those with urgency predominant incontinence received medications and behavioral/physical therapy. Currently, the primary surgical treatment of stress incontinence is midurethral slings. Greater than 66% of women undergoing midurethral sling surgery for stress incontinence also report baseline urgency incontinence. Investigators report improvement in urgency incontinence in some women with MUI undergoing midurethral sling, however, subjective outcomes are worse in women with MUI compared to pure stress incontinence and the lower cure rates are associated with persistent urgency incontinence. Studies also demonstrated that urgency incontinence is the major cause of patient dissatisfaction of surgery for stress incontinence and prolapse. Reduced satisfaction and treatment failure after midurethral sling surgery is associated with higher baseline urgency and urgency incontinence. Additionally, one study showed that 33% of women who did not have urgency incontinence symptoms prior to midurethral sling developed urgency symptoms after surgery. This study further complicates the issue, as it is possible that midurethral sling may cause urgency symptoms in some patients. Overall, studies have shown a wide range in improvement of urgency incontinence symptoms after midurethral sling placement between 46-74%. The wide range of anticipated improvement coupled with the not insignificant rate of de novo in urgency incontinence symptoms after midurethral sling, make counseling women with MUI contemplating surgery challenging. Essentially, surgeons can counsel women with MUI that although their stress incontinence symptoms are likely to improve after midurethral sling (90% satisfaction), their urgency incontinence may get better, stay the same, or get worse. Other strategies for treating MUI have also been proposed including treatment with anticholinergic medication in addition to traditional sling surgery. In an AHRQ funded study, anticholinergic medical therapy had minimal to moderate efficacy for treatment of urgency incontinence symptoms. Furthermore, many women taking anticholinergic medications suffer bothersome side effects, such as dry mouth and constipation, and over 50% stop taking the medication during their treatment course. In our prior work, we found that women treated with anticholinergic medications prior to traditional continence surgery were more likely to have urgency symptoms post-operatively, suggesting poorer outcomes in women with MUI. Understandably, patients with persistent urgency symptoms post-operatively are significantly less satisfied with their symptoms and surgical outcomes than patients who have complete resolution of their symptoms.

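### Does the unsourced 93% success rate for sling plus onabotulinumtoxinA undermine the sample size?

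*Protocol*

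**What the plan says.** The primary outcome is the PGI-I at 3 months, split so that the two best answers count as success. Protocol section 8.0 gives two literature rates. For the sling: "In a study of women with MUI undergoing retropubic midurethral sling, 66% of patients reported a PGI-I of" the two best categories. For the injection: "in a randomized trial of intravesical onabotulinumtoxinA 55% of participants had PGI-I scores of" the same two categories. The next sentence, introduced as an inference from these, assumes success "in 66% of women undergoing sling alone and 93% in those undergoing sling plus onabotulinumtoxinA, we will need to recruit 34 patients" in each group for 80% power.

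The SAP uses the same inputs ("Assuming 66% of women in the placebo group and 93% in the onabotulinumtoxinA group were" improved) with 34 per arm, 80% power and a 0.05 significance level. It describes the basis in general terms: "We based the sample size estimation off of previous studies assessing treatment of slings for mixed urinary incontinence and onabotulinumtoxinA injections for overactive bladder".

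Recruitment exceeds 34 per arm only to cover losses. The protocol says "Assuming a significant attrition rate, we will recruit approximately 100 women (50 in each arm"; the SAP says "If we assumed a 15% dropout rate, we aimed to recruit 78 participants (39 in each arm". The primary comparison is a chi-square test, significant at p of 0.05 or less. Neither document reports a success rate for the combined treatment, and neither mentions a risk difference or a confidence interval.

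**The concern.** A reader who meets 66% and 55%, then a word of inference, then 93%, expects a rule leading from the first two to the third. None is given: no combining formula, citation, pilot result or smallest important difference. The 93% is the one rate in the calculation without a stated origin, and it fixes the 27-point difference on which the 80% power rests.

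The figure is also demanding. If the injection leaves sling successes as successes, 93% requires about 79% of the women whom the sling alone fails to become successes, against a cited 55% for the injection by itself. If the true benefit were smaller, the trial could easily miss it. With only a test and a p-value threshold planned, a non-significant result might then be taken as evidence that the injection adds nothing.

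**Working it through.** **Inputs.** Success rates of 66% and 93% (protocol 8.0 and SAP); 34 per arm (both); 80% power (both); 0.05 (SAP, and the threshold for tests in protocol 8.0; the protocol's sample-size sentence prints 0.5). Two-sided testing is my assumption, as the chi-square test implies. Recruitment targets are 39 per arm (SAP) and 50 per arm (protocol).

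**Reproducing the plan's figure.** With pooled variance and no continuity correction, p̄ = (0.66 + 0.93)/2 = 0.795 and

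- s0 = √(2 × 0.795 × 0.205) = 0.5709
- s1 = √(0.66 × 0.34 + 0.93 × 0.07) = 0.5381
- n = [(1.96 × 0.5709 + 0.8416 × 0.5381)/0.27]² = (1.5718/0.27)² = 33.9, so 34 per arm
- Power at 34 = Φ[(0.27 × √34 − 1.96 × 0.5709)/0.5381] = Φ(0.846) = 80.1%

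The stated size and power are therefore correct for the stated rates. Exact power of the uncorrected chi-square test at 34 per arm is 83.3%, slightly better.

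**What 93% implies.** Let c be the share of sling failures that the injection turns into successes, with no sling success lost. The combined rate is 0.66 + 0.34c, so 93% needs c = 0.27/0.34 = 0.79. Taking c = 0.55 from the cited injection rate gives 0.66 + 0.34 × 0.55 = 84.7%, but only if that rate applies to sling failures, which the documents do not say. Without antagonism, 66% and 55% allow any combined rate from 66% to 100%.

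**Sensitivity, control fixed at 66%** (same formula; columns are evaluable women per arm):

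| Combined rate | 34 | 39 | 50 | n per arm for 80% power |
|---|---|---|---|---|
| 80% | 25% | 28% | 35% | 157 |
| 84.7% | 43% | 48% | 58% | 83 |
| 85% | 44% | 50% | 60% | 80 |
| 90% | 67% | 73% | 84% | 46 |
| 93% | 80% | 85% | 93% | 34 |

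The columns for 39 and 50 assume no losses.

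**Dependence on the control rate.** With the combination held at 93% and 34 per arm, power is about 91% if control is 60% and about 63% if it is 72%. The 93% is thus not the only input that moves the power.

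**Precision.** The 95% half-width of the risk difference is 1.96 × √[(0.66 × 0.34 + p(1 − p))/n]. At 34 per arm it is 18.1 points for p = 0.93 and 22.5 points if both arms are at 66%. At 50 per arm the figures are 14.9 and 18.6 points.

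**The case for a change.** The strongest case for a change is that a trial may choose an optimistic effect if it says so, whereas this plan presents the effect as drawn from earlier studies, and no reader can check that. Nor does the larger recruitment settle it: the extra women are there for attrition, and even 50 per arm with no losses gives only 58% power at 84.7%. On this view a sentence on the origin of 93%, a short power table and a planned risk difference with interval would cost almost nothing and would guard against misreading a null result.

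Much of this stands. The inferential wording in the protocol is not earned by what precedes it, the SAP's general reference to earlier studies does not fill the gap, and the sensitivity is large.

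What does not stand is the step to a required change.

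- Both documents put 93% forward with the word for an assumption, and the power they claim is the power delivered under it.
- The cited rates do not rule it out. Section 2.0 gives a reason why conversion among sling failures might exceed 55%: in women with mixed incontinence, "the lower cure rates are associated with persistent urgency incontinence", which is the symptom the injection targets. In the other direction, section 8.0 does not state the population behind the 55%, so it may not carry over at all.
- Power at other rates is not displayed, but the control rate, sample size, significance level and test are all stated, so anyone can compute it as above.
- The missing interval is a separate reporting matter that would exist whatever the source of 93%. Naming a chi-square test does not bar reporting proportions and their difference, and nothing in the plan says that a non-significant result will be read as no benefit.

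**Conclusion.** The observation is true, but it is a gap in justification, not an error in the plan. The calculation reproduces (34 per arm, 80.1% power), and 93% is unsupported but not contradicted. Sourcing the figure, or calling it a planning assumption for a 27-point difference from 66%, would alter no sample size, test, threshold or result.

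A reader of the results should keep the size of the dependence in mind. With control at 66%, two-sided 0.05 and 34 evaluable women per arm, power falls from 80% at a combined rate of 93% to about 67% at 90%, 44% at 85% and 25% at 80%. A non-significant chi-square result would therefore not exclude a worthwhile benefit. An analyst would sensibly report the two proportions and their difference with a 95% interval, with a half-width of about 18 to 23 points at 34 per arm and 15 to 19 at 50. The plan leaves room for that as it stands. These figures rest on the pooled-variance approximation and a 66% control rate; the 84.7% rate and the conversion shares are illustrations, not rates the documents support.
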